1. LIST OF ABBREVIATIONS

Table 1: List of Abbreviations

Abbreviation	Term
AE	Adverse Event
ALT	Alanine Aminotransferase
AST	Aspartate Aminotransferase
AUC	Area under the concentration-time curve
AUC _(0-∞)	AUC from time zero (pre-dose) extrapolated to infinite time
AUC _(0-τ)	AUC from time zero (pre-dose) to time of last observed quantifiable concentration within a subject across all treatments
BMI	Body mass index
C _{max}	Maximum observed concentration
CRF	Case Report Form
dy	Days
ECG	Electrocardiogram
g	Grams
ITT	Intent-to-Treat Population
Kg	Kilogram
mg	Milligrams
N	Total Sample Size
PK	Pharmacokinetic
s.d.	Standard Deviation
SAE	Serious Adverse Event
SAS	Statistical Analysis System
TGG	The Griesser Group
ULN	Upper Limit of Normal
WHO	World Health Organization

2. INTRODUCTION

The Drug Product ZYN002 is a transdermal cannabidiol (CBD) gel. CBD is the primary non-euphoric cannabinoid contained in the *Cannabis sativa L* plant. The CBD contained within ZYN002 is a pharmaceutically produced Active Pharmaceutical Ingredient (API) that is chemically identical to the CBD present in Cannabis.

CBD is the primary non-psychoactive cannabinoid found in the Cannabis plant. Cannabis has low affinity for CB₁ and CB₂ receptors, and CBD produces multiple effects, including blocking the equilibrative nucleoside transporter, the orphan G-protein receptor GPR 55, and the transient receptor potential of ankyrin type 1 channel, and regulating the intracellular effects of calcium. The influence of CBD on these targets, each of which is known to play a role in neuronal excitability, is the scientific basis for its antiepileptic potential. The expectation of a wide margin of safety in humans was founded on the results of well-controlled studies in which CBD has exhibited high tolerability across several modes of administration.

ZYN002 is being developed as a clear, transdermal gel to provide consistent, controlled cannabidiol (CBD) delivery with twice daily (every 12 hours [Q12 H]) dosing. Because CBD is virtually insoluble in water, ethanol and propylene glycol are used as solubilizing agents and diethylene glycol mono-ethyl ether (brand name: Transcutol[®] HP) is used as a permeation enhancer.

22q11.2 deletion syndrome, (also referred to as 22qDS or 22q) is the most common (yet under-diagnosed) microdeletion syndrome affecting 1 in 2,000 to 1 in 4,000 live births. Approximately 50 genes are affected resulting in effects on multiple body systems. 22q11.1DS is inherited as autosomal dominant but 90-95% cases are spontaneous ([McDonald-McGinn et al, 2015](#)). Patients usually harbor a 1.5 to 3 Mb hemizygous deletion at chromosome 22q11.2, resulting in pathognomonic T-Box Protein 1 (TBX1), adaptor protein CRKL and/or mitogen-activated protein kinase 1 (MAPK1) haplo-insufficiency. The clinical presentations of 22qDS are highly variable within and between families, even in identical twins. Each patient presents their own unique profile of symptoms and signs. Males and females are equally affected. Undiagnosed older children and adults are often only ascertained due to behavioral problems or school performance. In some cases, adults are only diagnosed when they have an affected child. Over 180 clinical features have been described in association with 22qDS, none of which in isolation is considered pathognomonic for the condition ([Koczkowska et al, 2017](#)).

There is a clear need for well-tolerated, pharmacological treatments that provide significant clinical benefits in terms of ameliorating anxiety and associated socio-behavioral deficits, while demonstrating minimal clinically relevant negative side effects.

3. STUDY OBJECTIVE(S) AND ENDPOINT(S)

3.1. Primary Study Objective

To evaluate the safety and tolerability of ZYN002 for up to 38 weeks, in patients ages 4 to < 18 years, in the treatment of symptoms of 22q.11.2 Deletion Syndrome (22qDS).

3.2. Secondary and Exploratory Study Objectives

Secondary:

- To evaluate the efficacy of ZYN002 in the treatment of symptoms of 22qDS.
- To evaluate CBD and THC plasma level exposure.

Exploratory:

The identification of plasma levels of CBD metabolite(s) may be conducted.

4. STUDY DESIGN

This is an open-label study to assess the safety, tolerability and efficacy of CBD administered as ZYN002, a transdermal gel, for the treatment of child and adolescent patients with 22q. Male and female patients with 22q will be treated in Period 1 for 14 weeks.

Patients with less than a 25% improvement from baseline in the ABC-C Irritability subscale may have their total dose increased by the investigator at Week 6.

Patients that have made a $\geq 35\%$ improvement on the ABC-C Irritability sub-scale will be allowed to continue to Period 2 for an additional 24 weeks of treatment. Only patients taking AED medications for treatment of seizures or epilepsy will have an additional one or two-week Taper Period.

Approximately 20 male and female patients, ages 4 to < 18 years, will receive ZYN002.

4.1. Definition of Study Drugs

This study has a 14-week treatment Period 1 and up to a 24-week extension (Period 2) as follows:

- Patients weighing ≤ 35 kg will receive 125 mg CBD applied Q12H (± 2 hours); total daily dose of 250 mg CBD. Each application will consist of **one sachet** of ZYN002 CBD 4.2% concentration, containing 2.98 g of gel. At Week 6, if the patient has less than a 25% improvement from baseline in the ABC-C irritability sub-scale, the investigator may increase the dose as follows:
 - Patients weighing ≤ 35 kg receiving a total daily dose of 250 mg CBD may increase to a daily dose of 500 mg. Each application will consist of **two sachets** of ZYN002 CBD 4.2% concentration, containing 2.98 g of gel.
- Patients weighing > 35 kg will receive 250 mg CBD applied Q12H (± 2 hours); for a total daily dose of 500 mg CBD. Each application will consist of **two sachets** of ZYN002 CBD 4.2% concentration, each sachet containing 2.98 g of gel. At Week 6, if the patient has less than a 25% improvement from baseline in the ABC-C irritability sub-scale, the investigator may increase the dose as follows:
 - Patients weighing > 35 kg receiving a total daily dose of 500 mg CBD may increase the daily dose to 750 mg. Each application will consist of **three sachets** of ZYN002 CBD 4.2% concentration, containing 2.98 g of gel.

Should the weight of the patient change from visit to visit the dose may be adjusted at the discretion of the investigator.

4.2. Sample Size Considerations

4.2.1. Sample Size Justifications

This study is exploratory in nature and as such, no formal sample size was determined. This is the first study of ZYN002 being used for the indication of 22q. The sample size of 20 patients was deemed large enough to provide a reliable answer for the study objectives.

4.3. Randomization

N/A open label.

4.4. Clinical Scales and Questionnaires

The study questionnaires and scales administered are outlined in [Table 2](#).

Table 2: ZYN2-CL-031 Scales and Questionnaires Administered

Scale	Screening	Visit 2, Day 1	Visit 3, Week 6	Visit 4, Week 14	Visit 5, Week 22	Visit 6, Week 30	Visit 7, Week 38	ET
Aberrant Behavior Checklist (ABC-C)	X	X	X	X	X	X	X	X
Autism Diagnostic Observation Schedule®-2 (ADOS®-2)	X							
Anxiety, Depression and Mood Scale (ADAMS)	X		X	X	X	X	X	X
Clinical Global Impression-Severity (CGI-S)	X	X	X	X	X	X	X	X
Clinical Global Impression-Improvement (CGI-I)			X	X	X	X	X	X
Columbia-Suicide Severity Rating Scale – Children’s version (C-SSRS)	X	X	X	X	X	X	X	X
Pediatric Anxiety Rating Scale – Revised (PARS-R)	X	X	X	X	X	X	X	X
Qualitative Caregiver Reported Behavioral Problems Survey	X		X	X	X	X	X	X
Children’s Sleep Habit Questionnaire (CSHQ)	X			X			X	X

Assessments completed at Screening are found in [Table 3](#), assessments completed for Period 1 are found in [Table 4](#), and assessments completed for Period 2 are found in [Table 5](#).

Table 3: Schedule of Assessments – Screening (Visit 1).

Study Procedures	Screening Visit Days -28 to Day -8
Informed Consent	X
Review Eligibility Criteria	X
Medical History	X
Demographics	X
Concomitant Medications	X
Complete Physical / Neurological Exam ^a	X
Confirm 22qDS Diagnosis	X
Confirm Epilepsy Diagnosis	X
Vital Signs	X
12-lead ECG ^b	X
HIV-Ab 1+2 + Hepatitis B+C	X
Laboratory Tests and Urinalysis	X
Pregnancy Test (females)	X
Drug Screen (Urine and Blood)	X
Aberrant Behavior Checklist-Community (ABC-C)	X
Autism Diagnostic Observation Schedule [®] -2 (ADOS [®] -2) ^c	X
Clinical Global Impression-Severity (CGI-S)	X
Columbia-Suicide Severity Rating Scale – Children’s version (C-SSRS)	X
Anxiety, Depression and Mood Scale (ADAMS)	X
Qualitative Caregiver Reported Behavioral Problems Survey	X
Children’s Sleep Habit Questionnaire (CSHQ)	X
Pediatric Anxiety Rating Scale (PARS-R)	X
CBD/THC PK Sample	X
AED Blood Sample ^d	X
Skin Assessment Exam ^e	X
Adverse Event Review	X
Optional: DNA for genomic screening	Optional

Note: There must be at least 7 days between Visit 1 (Screening) and Visit 2 (Day 1).

Table 4: Period 1 Schedule of Assessments – 14-Week Treatment Period

Study Procedures	14-Week Treatment Period 1 Visit Schedule			Taper Period, If Applicable		Study Visit Week 16 or Week 17 for AED Patients Tapering Study Drug ^a	Un- scheduled Visit(s)	Week 10 Telephone Follow-up
	Visit 2	Visit 3 Week 6	Visit 4 Week 14 EOS/ET ^a	Week 15	Week 16			
	Day 1	(± 3 days)	(± 3 days)	(± 3 days)	(± 3 days)			
	Study Drug Dosing			Tapered 50% each week. No Study Visit				
Review Eligibility Criteria	X							
Concomitant Medications	X	X	X			X	X	X
Physical/Neurological Exam ^b	X	X	X			X		
Vital Signs ^c	X	X	X			X	X	
12-lead ECG ^d	X	X	X					
Laboratory Tests and Urinalysis		X	X					
Pregnancy Test ^e		X	X			X		
CBD/THC PK Blood Sample		X	X					
Blood Sample Valproic Acid ^f		X	X					
ABC-C	X	X	X					
CGI-S	X	X	X					
CGI-I		X	X					
ADAMS	X	X	X					

Table 4: Period 1 Schedule of Assessments – 14-Week Treatment Period, cont’d								
Study Procedures	14-Week Treatment Period – Visit Schedule			Taper Period, If Applicable		Study Visit Week 16 or Week 17 for AED Patients Tapering Study Drug ^a Visit ^a	Un- scheduled Visit(s)	
	Visit 2	Visit 3 Week 6	Visit 4 Week 14 EOS/ET ^a	Week 15	Week 16			Week 10 Telephone Follow- up ¹
	Day 1	(± 3 days)	(± 3 days)	(± 3 days)	(± 3 days)			
	Study Drug Dosing			Tapered 50% each week. No Study Visit				
C-SSRS	X	X	X			X	X	
Qualitative Caregiver Behavioral Problems/Improvements Survey		X	X					
Children’s Sleep Habit Questionnaire			X					
Pediatric Anxiety Rating Scale - Revised	X	X	X					
Instruct Parent/caregiver on Study Drug Application ^g	X							
Daily Study Drug Application ^h	X	X	X	X	X			
Skin Assessment Exam ⁱ	X							
Parent/caregiver Completes Daily Skin Irritation Diary ^j	X	X	X	X	X	X	X	
Review Patient Skin Irritation Diary		X	X			X	X	
Skin Irritation Exam ^k		X	X			X	X	X
Adverse Event Review	X	X	X			X	X	X

Table 5 Footnotes - Period 1:

- a. All patients will have a Week 14 Visit/ET. All patients that do not qualify for Period 2 will have an End of Study Visit at Week 14. AED patients will taper study drug for 1 or 2 weeks after the EOS Visit and return on Week 16 or 17 for final discharge from the study.
- b. For patients that do not qualify for Period 2, Week 14/Visit 4 EOS/ET patients will have both weight and height taken. For patients taking AEDs and returning on Week 16 or 17 to be discharged from the study, a targeted physical examination (heart, lungs, abdomen and extremities) may be performed, if the investigator deems clinically relevant.
- c. Vital signs (including blood pressure, heart rate, respiratory rate, and infrared forehead or oral or tympanic temperature) will be recorded after the patient has been sitting for at least 5 minutes. Vital signs will be assessed at each study visit pre-dose.
- d. One ECG to be collected prior to starting treatment (Screening or Visit 2), provided that ECG is normal or has a finding that is not clinically significant.
- e. A pregnancy test will be completed at Week 6, and Week 14/EOS/ET for all females of childbearing potential. Pregnancy tests can be plasma or urine.
- f. Patients receiving valproate or valproic acid will have a blood sample drawn for plasma level of valproic acid. Where possible, effort should be made to get a trough sample. If not, the AED morning dose may be administered prior to the clinic visit. The time of the prior dose of study drug and valproate/valproic acid, if applicable in addition to the time of each blood sample collection will be recorded. During the Treatment Period valproic acid (for patients receiving valproate or valproic acid) blood samples will be taken at Week 6, and Week 14.
- g. On Day 1 the parent/caregiver will be instructed on how to complete the daily skin irritation diary. Scoring of skin irritation will start the evening of Day 1 through discharge from the study by the parent/caregiver. The site will evaluate the parent/caregiver applying the study treatment at each study visit and provide feedback/additional instruction as applicable.
- h. At Weeks 6, and 14 parents/caregivers will administer the dose in the clinic after they have their PK and valproic acid (for patients taking valproate/valproic acid) blood drawn. At Week 14 patients who require a tapering period will be provided a 1 or 2-week supply of study treatment.
- i. A skin assessment examination will be completed by the Investigator at Day 1 pre-dose. Shoulders and upper arms will be examined to determine there are no skin disease or condition, including eczema, psoriasis, melanoma, acne, contact dermatitis, scarring, imperfections, lesions, tattoos, or discoloration that may affect treatment application, application site assessments, or affect absorption of the study drug where study drug could be applied.
- j. Parents/caregivers will assess the application site daily and record all irritation scores in their daily skin irritation diary, starting with the PM dose on Day 1. When irritation exists, efforts will be made to apply the gel to a non-irritated area of the upper arms/shoulders and/or right and left upper thighs. Temporary application to the upper thighs can only be used after consultation with the investigator. If the skin irritation score is greater than "2", the patient will contact the Investigator to determine if an Unscheduled Visit is required.
- k. The investigator will perform a skin irritation examination pre-dose at study Visits 3, Visit 4/EOS/ET and Unscheduled Visits. The parent/caregiver will also be asked about the patients skin irritation at the Week 10 Telephone Follow-up call.
- l. A Telephone Follow-Up will occur for those patients whose dose was increased at Week 6.

Table 5: Period 2 Schedule of Assessments – 24-Week Extension Treatment

Study Procedures	24-Week Treatment Period 2 Visit Schedule			Taper Period, If Applicable		Study Visit Week 40 or Week 41 for AED Patients Tapering Study Drug ^a	Un-scheduled Visit(s)
	Visit 5 Week 22	Visit 6 Week 30	Visit 7 Week 38 EOS/ET ^a	Week 39	Week 40		
	(± 3 days)	(± 3 days)	(± 3 days)	(± 3 days)	(± 3 days)		
	Study Drug Dosing			Tapered 50% each week. No Study Visit			
Concomitant Medications	X	X	X			X	X
Physical/Neurological Exam ^b			X			X	
Vital Signs ^c	X	X	X			X	X
12-lead ECG			X				
Laboratory Tests and Urinalysis			X				
Pregnancy Test ^d			X			X	
CBD/THC PK Blood Sample			X				
Blood Sample for Valproic Acid ^{e, g}			X				
ABC-C	X	X	X				
CGI-S	X	X	X				
CGI-I	X	X	X				
ADAMS	X	X	X				

Table 6: Period 2 Schedule of Assessments – 24-Week Extension Treatment Period, cont'd							
Study Procedures	24-Week Treatment Period – Visit Schedule			Taper Period, If Applicable		Study Visit Week 40 or Week 41 for AED Patients Tapering Study Drug ^a Visit ^a	Un-scheduled Visit(s)
	Visit 5 Week 22 (± 3 days)	Visit 6 Week 30 (± 3 days)	Visit 7 Week 38 EOS/ET ^a (± 3 days)	Week 39 (± 3 days)	Week 40 (± 3 days)		
	Study Drug Dosing			Tapered 50% each week. No Study Visit			
C-SSRS	X	X	X			X	X
Qualitative Caregiver Behavioral Problems/Improvements Survey	X	X	X				
Children’s Sleep Habit Questionnaire			X				
Pediatric Anxiety Rating Scale-Revised	X	X	X				
Daily Study Drug Application	X	X	X	X	X		
Parent/caregiver Completes Daily Skin Irritation Diary ^{f, h}	X	X	X	X	X	X	X
Review Patient Skin Irritation Diary	X	X	X			X	X
Skin Irritation Exam ⁱ			X			X	X
Adverse Event Review	X	X	X			X	X

Table 6 Footnotes - Period 2:

- a. Patients who withdraw prior to Period 2 Week 38 will complete the EOS/ET at Week 38. AED patients will taper study drug for 1 or 2 weeks after the EOS Visit and return on Week 40 or 41 for final discharge from the study, unless they are transitioning to receive drug through Special Access.
- b. Patients will have both weight and height taken at EOS/ET. For patients taking AEDs and returning on Week 40 or 41 to be discharged from the study, a targeted physical examination (heart, lungs, abdomen and extremities) may be performed, if the investigator deems clinically relevant.
- c. Vital signs (including blood pressure, heart rate, respiratory rate, and infrared forehead or oral or tympanic temperature) will be recorded after the patient has been sitting for at least 5 minutes. Vital signs will be assessed at each study visit pre-dose.
- d. A pregnancy test will be completed at Week 38/EOS/ET for all females of childbearing potential. Pregnancy tests can be plasma or urine.
- e. Patients will have a blood sample drawn for plasma level of valproic acid (for patients taking valproate or valproic acid) at Week 38/Visit 7. Where possible, effort should be made to get a trough sample for the valproic acid (for patients receiving valproate/valproic acid). If not, the AED morning dose may be administered prior to the clinic visit. The time of the prior dose of study drug and valproic acid (if applicable) in addition to the time of each blood sample collection will be recorded.
- f. Scoring of skin irritation will start the evening of Day 1 through discharge from the study by the parent/caregiver. The site will evaluate the parent/caregiver applying the study treatment at each study visit and provide feedback/additional instruction as applicable.
- g. At Week 38, parents/caregivers will administer the dose in the clinic after they have their PK and valproic acid (for patients taking valproate or valproic acid) blood drawn. At Week 38 patients who require a tapering period will be provided a 1 or 2-week supply of study treatment.
- h. Parents/caregivers will assess the application site daily and record all irritation scores in their daily skin irritation diary, starting with the PM dose on Day 1. When irritation exists, efforts will be made to apply the gel to a non-irritated area of the upper arms/shoulders and/or right and left upper thighs. Temporary application to the upper thighs can only be used after consultation with the investigator. If the skin irritation score is greater than “2”, the patient will contact the Investigator to determine if an Unscheduled Visit is required.
- i. The investigator will perform a skin irritation examination pre-dose at study Visit 7 EOS/ET and Unscheduled Visits. Weeks 5 and 6 the patient can receive their morning dose at home.

5. PLANNED ANALYSES

5.1. Planned Interim Analyses

An interim analysis is planned at the conclusion of Period 1 (treatment week 14/Visit 4):

- | | |
|--------------------------------------------------|--------------|
| • Estimated Last patient enrolled | 21 Feb 2022 |
| • Estimated Last patient completing Period 1 | 31 May 2022 |
| • Database Lock Period 1 | 06 June 2022 |
| • Estimated Release of study Tables and Listings | 10 June 2022 |

Data to be evaluated for interim analysis include the following.

- Disposition
- Demographics
- Baseline Characteristics
- Adverse Events
- Medical History
- Concomitant Medications
- Laboratory Data
- C-SSRS Data
- Efficacy scale data for Period 1 for the following scales and questionnaires:
 - ABC-C
 - ADAMS
 - CGI
 - PARS-R

The specific displays to be generated in Period 1 are identified with an “X” in [Section 11](#). Any additional data required for the interim analysis will be produced by an Adhoc Summary Table.

5.2. Data included in Period 1 Analyses

The records to be included in the Period 1 analyses will include all records with a nominal visit of ≤ 4 (Week 14/ET). All summaries will include one column only identified as ZYN002.

In an attempt to include all Period 1 Concomitant Medications and Adverse Events in the Period 1 analyses TGG will need to calculate a Week 14 Date for both subjects who completed Period 1 and who discontinued in Period 1 before Week 14. This will be accomplished by the following steps using the last non-missing value as the actual or imputed Week 14 date:

- a) If a subject completes Period 1 then use their actual Week 14 Date.
- b) If a subject discontinues before Week 14 date and their last nominal visit is identified as Week 14/ET then add ‘X’ days to that date to get to Day 98 (7 times 14).
- c) If Week 6, TGG will impute the Week 14 cutoff date to be the Week 6 date plus (7 times 8) to get the Week 14 imputed Date

d) If Day 1, TGG will impute the Week 14 date to be Day 1 plus (7 times 14)

Treatment emergent adverse events and concomitant medication summaries will include start dates that occur any time before treatment begins and treatment ends. Refer to [Section 6.2.3](#).

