| Parent/caregiver Completes Daily Skin Irritation Diary ^j | X | X | X | X | X | X | X | |
| Review Patient Skin Irritation Diary | | X | X | | | X | X | |
| Skin Irritation Exam ^k | | X | X | | | X | X | X |
| Adverse Event Review | X | X | X | | | X | X | X |

Table 5 Footnotes - Period 1:

- a. All patients will have a Week 14 Visit/ET. All patients that do not qualify for Period 2 will have an End of Study Visit at Week 14. AED patients will taper study drug for 1 or 2 weeks after the EOS Visit and return on Week 16 or 17 for final discharge from the study.
- b. For patients that do not qualify for Period 2, Week 14/Visit 4 EOS/ET patients will have both weight and height taken. For patients taking AEDs and returning on Week 16 or 17 to be discharged from the study, a targeted physical examination (heart, lungs, abdomen and extremities) may be performed, if the investigator deems clinically relevant.
- c. Vital signs (including blood pressure, heart rate, respiratory rate, and infrared forehead or oral or tympanic temperature) will be recorded after the patient has been sitting for at least 5 minutes. Vital signs will be assessed at each study visit pre-dose.
- d. One ECG to be collected prior to starting treatment (Screening or Visit 2), provided that ECG is normal or has a finding that is not clinically significant.
- e. A pregnancy test will be completed at Week 6, and Week 14/EOS/ET for all females of childbearing potential. Pregnancy tests can be plasma or urine.
- f. Patients receiving valproate or valproic acid will have a blood sample drawn for plasma level of valproic acid. Where possible, effort should be made to get a trough sample. If not, the AED morning dose may be administered prior to the clinic visit. The time of the prior dose of study drug and valproate/valproic acid, if applicable in addition to the time of each blood sample collection will be recorded. During the Treatment Period valproic acid (for patients receiving valproate or valproic acid) blood samples will be taken at Week 6, and Week 14.
- g. On Day 1 the parent/caregiver will be instructed on how to complete the daily skin irritation diary. Scoring of skin irritation will start the evening of Day 1 through discharge from the study by the parent/caregiver. The site will evaluate the parent/caregiver applying the study treatment at each study visit and provide feedback/additional instruction as applicable.

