11.5. Reporting Adverse Events

If any protocol defined expedited event, or serious, life-threatening, or fatal AE occurs whether related to study drug or not, the Investigator must notify the Sponsor within 24 hours by telephone and email.

24 Hour SAE [contact]

Email: [contact]

The definition for a ‘protocol defined expedited event’ for the purposes of this study is a Skin Irritation score of ‘4’, “intense erythema with edema and blistering/erosion” (see [Table 7](#)).

The Investigator must complete, sign and date the SAE pages, verify the accuracy of the information recorded on the SAE pages with the corresponding source documents, and send a copy by email to the Sponsor.

Additional follow-up information, if required or available, should all be emailed to the Sponsor within one business day of receipt and this should be completed on a follow-up SAE form and placed with the original SAE information and kept with the appropriate section of the CRF and/or study file.

All SAEs (related and unrelated) will be followed from the signing of the ICF until the End of Study Visit, 30 days post last dose of study drug or the patient is lost to follow up (whichever comes last). Any SAEs considered possibly or probably related to the investigational product and discovered by the Investigator up to 30 days after the study should be reported. All SAEs must be reported to the Sponsor within one business day of the first awareness of the event. The Investigator must complete, sign and date the SAE pages, verify the accuracy of the information recorded on the SAE pages with the corresponding source documents, and send a PDF copy by email to the Sponsor.

The Sponsor representative is responsible for notifying the relevant regulatory authorities of certain events. It is the Investigator’s responsibility to notify the HREC of all SAEs that occur at his or her site. Investigators will also be notified of all unexpected, serious, drug-related events (7/15 Day Safety Reports) that occur during the clinical study. Each site is responsible for notifying its HREC of these additional SAEs.

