8.1.1. Adverse Events

All adverse events will be coded using the Medical Dictionary for Regulatory Activities (MedDRA) Version 21.0 or greater. Treatment emergent adverse events (TEAEs) are defined as adverse events with onset dates on or after the first dose of study drug.

All AE summaries will include total number of TEAEs and total number of patients with AEs.

An overall summary of adverse events will include number (%) of patients reporting ≥ 1 TEAE (and number of TEAEs), TEAE by Severity (and number of TEAEs), treatment-related TEAEs (and number of TEAEs), SAEs (and number of TEAEs), TEAE by outcome (and number of TEAEs), TEAEs that resulted in treatment discontinuation (and number of TEAEs). In addition, the total number of TEAEs by subject will be summarized.

Additionally, summaries will be presented for all TEAEs by system organ class and preferred term (overall and by severity). TEAEs determined by the investigator to be treatment-related (overall and by severity). Serious AEs will also be summarized. Adverse events causing permanent discontinuation from treatment will be summarized, fatal adverse events will be summarized, and TEAEs by preferred term in descending order will be summarized.

The incidence of adverse events will be summarized using descriptive statistics by system organ class and preferred term. Patients are counted only once in each system organ class category, and only once in each preferred term category. Treatment-related adverse event summaries will include adverse events with missing relationship to study drug. For the summaries by severity, patients and TEAEs are counted at the greatest severity.

AEs will be summarized separately for each treatment Period (1, 2) and overall (the whole study).

Listings for fatal AEs, serious AEs, and AEs leading to discontinuation, will also be presented.

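### SAP 5.2 closes Period 1 at Week 14 for every completer, so taper-phase TEAEs and post-dose SAEs of patients who do not enter Period 2 fall outside the Period 1 tables and have no defined period

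*SAP*

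**What the plan says.** SAP 5.2 derives a Week 14 date for each patient so as to decide which events belong to Period 1. Its stated aim begins "In an attempt to include all Period 1 Concomitant Medications and Adverse Events in the Period 1 analyses". Visit-based records are also limited: the Period 1 analyses "will include all records with a nominal visit of ≤ 4 (Week 14/ET"). The date rules are:

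- Rule (a), completers: "If a subject completes Period 1 then use their actual Week 14 Date".
- Rule (b), patients who stop early and whose last visit is labelled Week 14/ET: days are added "to that date to get to Day 98 (7 times 14").
- Rules (c) and (d), patients last seen at Week 6 or Day 1: the date is imputed forward by 8 or 14 weeks.

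SAP 8.1.1 then states that "AEs will be summarized separately for each treatment Period (1, 2) and overall (the whole study"). Section 11 of the SAP lists separate TEAE and SAE tables for each.

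The documents foresee events after Week 14 in patients who do not continue. Under Protocol Table 5, footnote a (repeated in the SAP), patients not qualifying for Period 2 have their End of Study visit at Week 14, and "AED patients will taper study drug for 1 or 2 weeks after the EOS Visit and return on Week 16 or 17". Protocol 11.2.1.1 collects AEs up to discharge. Protocol 11.5 says SAEs "will be followed from the signing of the ICF until the End of Study Visit, 30 days post last dose of study drug", or loss to follow-up, taking the latest of these. SAP 6.2.4 puts no end limit on what counts as treatment-emergent.

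**The concern.** Rule (a) makes no distinction between a completer who starts Period 2 drug and one whose study ends at Week 14. For the first, the Week 14 date is a sensible boundary. For the second, it cuts off time in which the patient may still be applying tapered drug, and all of the SAE follow-up after the last dose.

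This also conflicts with the schedule. Protocol Table 5 and SAP Table 4 place the Week 15 and Week 16 taper columns, with daily drug application marked, and the Week 16/17 visit, with AE review marked, inside the Period 1 schedule.

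Early dropouts are treated the opposite way: the Period 1 window is carried forward over time when they are off drug. One Period 1 table therefore mixes two follow-up rules. Safety and tolerability is the primary objective, and entry to Period 2 requires a 35% irritability improvement, so the patients whose late events are left without a period are mainly those who improved less.

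**Working it through.** **Inputs.** Day numbering follows SAP 6.1.1 (date minus Day 1, plus 1). The cut-off rules come from SAP 5.2. The taper length (1 or 2 weeks) and return visit (Week 16 or 17) come from Protocol Table 5, footnote a. SAE follow-up of 30 days after the last dose comes from Protocol 11.5.

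**The plan's own figure.** 7 × 14 = 98, so rule (b) gives Day 98 as stated. Rule (d) adds 98 days to Day 1, which is Day 98 + 1 = Day 99. Rule (c) adds 56 days to the Week 6 date. If that visit is 42 days after Day 1, the result is 42 + 56 + 1 = Day 99. Hence about Day 98; the one-day difference is immaterial.

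**Completers who do not continue.** Period 1 extends 0 days past the Week 14 date. The follow-up that the protocol requires past that date is:

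| Patient | Days still on drug | Days to discharge visit (AEs) | Days of SAE follow-up (at least) |
|---|---|---|---|
| No taper | 0 | 0 | 0 + 30 = 30 |
| 1-week taper | 7 | (16 − 14) × 7 = 14 | 7 + 30 = 37 |
| 2-week taper | 14 | (17 − 14) × 7 = 21 | 14 + 30 = 44 |

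**Early dropouts.** Days after the last dose that the rule admits to Period 1 = 98 − day of last dose. Two illustrative values:

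- Last dose on Day 43: 98 − 43 = 55 days.
- Last dose on Day 84: 98 − 84 = 14 days.

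These are days the rule would accept, not days certain to be observed, since routine AE collection stops at discharge.

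**Where the excluded events go.** They meet the TEAE definition in SAP 6.2.4, so they enter the overall tables (for example 14.3.2.1.3 and, for SAEs, 14.3.2.6.3) and Listings 16.18.1 and 16.18.3. By rule (a) they are not in the Period 1 tables (14.3.2.1.1, 14.3.2.6.1). For the Period 2 tables (14.3.2.1.2, 14.3.2.6.2) the SAP gives no start or end rule, so their status there is undefined.

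**What cannot be computed.** The documents give neither the number of completers who do not continue nor the number of AED users. No count of affected patients or events can be derived.

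**The case against.** The strongest reply is that the data are complete and only a label is unclear. The overall tables cover the whole safety set, and the listings show every event. A reader might infer from the Period 1 cut-off that these events disappear from the safety report. They do not, and this part of the reply stands.

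A reader might also infer that the events will be tabulated under Period 2, for patients who never entered it. That would follow only if Period 2 were programmed as everything after the Week 14 date, and no text says so.

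The last sentence of SAP 5.2 points the other way: the TEAE and medication "summaries will include start dates that occur any time before treatment begins and treatment ends". It is garbled, but one reading takes the end of treatment as the bound, and together with the schedule it could lead a programmer to keep taper events in Period 1. It names no period, however, conflicts with rule (a), and would not reach SAEs after the last dose.

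Three further points limit the weight:

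- **Size.** In the earlier fragile X study, 5 of 18 completers (28%) did not enter the extension. It is tempting to carry that over, but that extension was optional with no response threshold stated, so it does not support a figure here. The taper group may be very small: several AEDs are excluded, and the detailed taper text in Protocol 7.8 addresses only valproate/valproic acid users, whereas the Table 5 footnote speaks of AED patients generally. Those passages need reconciling.
- **Interim lock.** The Period 1 lock (06 June 2022) is 6 days after the estimated last completion (31 May 2022), hence 30 − 6 = 24 days before a 30-day SAE window closes. This is not a defect. Any interim cut truncates follow-up, and the final lock is estimated for 14 December 2022.
- **Note to File.** The note effective 16 February 2026 describes a single arm rather than presentation by dose or by period. If by-period tables are dropped, the effect is confined to the Period 1 analysis. The note leaves the SAP text unchanged.

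After all this, a stated rule still excludes on-drug taper events that the schedule places in Period 1, and no rule assigns post-dose SAEs to a period.

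**Conclusion.** The point holds, within limits. For completers who do not enter Period 2, the Period 1 AE and SAE tables omit TEAEs during the Week 15-16 taper and up to discharge (14 or 21 days, tapering patients only). They also omit SAEs after the last dose (through at least 30 days past Week 14, or 37 or 44 with a taper). The SAP assigns these events to no period, while it credits early dropouts with off-drug time to about Day 98.

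The defect is one of allocation in the by-period tables. Overall safety counts are unaffected. The day counts assume that the last dose is at the Week 14 visit or at the end of the taper. The conclusion also takes SAP 5.2 as the definition of Period 1 for the final tables as well as the interim, since Section 8 gives no other. The practical effect may be small, but it bears on the trial's primary objective and is cheap to remove.

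**What to change.** In SAP 5.2 and 8.1.1, state an event window for each period:

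- Use the Week 14 date as the Period 1 cut-off only for patients who receive Period 2 drug.
- For all other patients, count TEAEs through the end of the taper or discharge in Period 1. This also covers early dropouts, so the forward imputation is no longer needed for their adverse events.
- Show SAEs starting after the last dose in a labelled post-treatment follow-up category, each counted once. Pooling them into Period 1 would give non-continuers 30 to 44 extra days in the same column as continuers whose window stops at Week 14.
- Restrict Period 2 tables to patients who received Period 2 drug.

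The cost is a short SAP insertion and one programming flag, with no change to data collection or patient care. There are two downsides. Final Period 1 counts may differ slightly from the interim. Follow-up length in Period 1 will still differ between continuers and non-continuers, which a table footnote should state.
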